If a participant develops nausea or diarrhea anytime during the first week on MMF 500 mg daily, we will offer the participant a change from MMF 500 mg daily to Myfortic© 360 mg daily. Myfortic© is an enteric coated version of MMF which is associated with less nausea and diarrhea in certain patients. If the participant tolerates the first week of Myfortic© 360 mg daily, then we will switch to Myfortic© 360 mg twice daily during the second week. If this is tolerated, then we will test for an anti-proliferative effect per protocol.

In the case of refractory nausea or diarrhea after week one, participants will be offered a change from MMF 500 mg twice daily to Myfortic© 360 mg twice daily. If a study participant is on MMF 750 mg twice daily, then we will switch to Myfortic© 540 mg twice daily. Participants will always have the option of withdrawing their participation from the trial rather than switching to Myfortic©.

Follow-up Visits (approximately 30 minutes)

Over the course of the study, we will ask participants to come in 19 more times (**Table 2**). Starting at entry, for the first month, we will ask them to come in weekly, then every other week for two months, then every month for the rest of the first 12 months, then at month 15, month 18½, and a final visit at 22 months. The purpose of these visits is to obtain samples to measure how the drug is affecting the HIV reservoir and to check safety labs.

We will check to see if the amount of HIV infected cells is decreasing after one year and after two years. If not, then we will ask the participant to stop participating in the study as we wish to see an effect of the drug at that point in time.

Influenza vaccination will occur at one follow-up visit unless study participants have already received this vaccine in the community.

During these visits, we will do the following:

Clinical Protocol

- 1) Draw between 6.5 and 255 mL of blood depending on visit (**Table 2**).
- 2) Draw 2 sets of blood separated by an hour to obtain peak and trough drug levels (weeks, 12, 24, 48, 74 & 88).
- 3) Perform follow up urine pregnancy testing in female participants (point-of-care-test in the clinic)
- 4) Ask how the participant is tolerating the study medication
- 5) Answer any questions
- 6) Discuss continuation in the study
- 7) Perform a focused physical exam as needed

Optional Rectal Biopsy Visit (up to 2 hours)

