6.4 Criteria for Treatment and Individual Study Participant Discontinuation

- The subject requires treatment with disallowed medications
- Pregnancy
- Nausea, vomiting or diarrhea refractory to anti-emetic medications
- Drug toxicity that requires permanent study drug discontinuation as defined in Section 6.2.
- If a participant does not plan to continue with the study
- Go / no-go criterion at month 12: participants must have at least a 0.25 log reduction from baseline at 12 months to continue on MMF. If this criterion is not met, participants will continue to be followed off study drug.
- Subject stops their antiretroviral therapy regimen for greater than 2 weeks
- The subject refuses further treatment and/or follow-up evaluations and decides to discontinue participation in the study
- The investigator determines that further participation would be detrimental to the subject's health or well-being
- The subject experiences virologic failure. Virologic failure will be managed according to local guidelines. In this study, virologic failure is defined as plasma HIV RNA \geq 1,000 copies/mL (confirmed by repeating the assay on 2nd aliquot of the same specimen). If a participant has a viral load between 500-1000 HIV RNA copies, then we will call the participants for an immediate recheck of their viral load as soon as possible and will continue to do so, until this value normalizes or meets criteria for virologic failure. Of note, viral load may be checked by the participant's primary care provider outside of the study: these values will be available to the study PI and the criteria for virologic failure will be the same.
- The subject fails to comply with the study requirements so as to cause harm to him/herself or seriously interfere with the validity of the study results

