6.6 Protocol for Study Discontinuation

Participants who withdraw from the study based on criteria described in sections 6.4 and 6.5 will be asked to return for a clinic visit for laboratory and safety tests. This procedure will continue until normalization of test results.

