9.0 HUMAN SUBJECTS

Participant will be 5 adults and children ≥ 18 and ≤ 65 years of age. Participants will have received ART for at least 2 years with demonstration of full viral suppression during this time, documented by at least four negative plasma viral loads and no more than one plasma viral blip during this time. They will also have a current CD4+ T cell count of $\geq 350/\mu\text{l}$. The participants will receive 500mg MMF twice daily in addition to their ART regimen. The planned MMF treatment duration is 22 months, but efficacy Go/no-Go algorithms at the end of month 12 may lead to earlier termination of MMF treatment in some or all study participants.

All study participants must plan to reside in the Seattle area for the duration of the study. We anticipate pre-screening 30 potential study participants by medical charts to identify 15 who will be approached by study staff to schedule an in-person eligibility visit; the first 5 available study candidates will enter the anti-proliferation test phase receiving MMF for one week. We conservatively estimate that 1 of these 5 individuals will fail to document adequate T cell anti-proliferation and not be enrolled in this study. We will continue to screen and test until we enroll 5 participants with a verified in vivo anti-proliferative effect of MMF, who will then continue to take MMF for 22 months. Participants who discontinue MMF treatment due to inadequate efficacy in reducing the latent HIV reservoir at the 12 month Go/no-Go decision point, or due to treatment related side effects, will not be replaced.

Potential Risks include:

(1) Stress and anxiety could result from study participation. These will be minimized by careful explanation of study procedures, and maintenance of an open, supportive attitude by study personnel.

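### Section 6.1 asks a participant who fails the one-year reservoir check to leave the study, 6.4 keeps them in follow-up off MMF, and 8.6 has no rule for the off-drug data

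*Combined protocol and SAP*

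**What the plan says.** Section 6.1 (Follow-up Visits) states: "We will check to see if the amount of HIV infected cells is decreasing after one year and after two years". The next sentence gives the consequence: "If not, then we will ask the participant to stop participating in the study".

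Section 6.4 sets the go/no-go rule: "participants must have at least a 0.25 log reduction from baseline at 12 months to continue on MMF". Its consequence is different: "If this criterion is not met, participants will continue to be followed off study drug".

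Section 8.1 treats the rule as a condition for staying in the MMF arm. Section 9.0 says that the month-12 decision "may lead to earlier termination of MMF treatment in some or all study participants". Both concern treatment and are silent on leaving the study. Section 9.0 adds that "Participants who discontinue MMF treatment due to inadequate efficacy in reducing the latent HIV reservoir at the 12 month Go/no-Go decision point" are not replaced.

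Section 6.6 covers "Participants who withdraw from the study based on criteria described in sections 6.4 and 6.5", who "will be asked to return for a clinic visit for laboratory and safety tests" until results normalise.

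Section 8.6 plans a separate regression for each participant with time alone as covariate, and a mixed model on the pooled data with a time-by-arm interaction. It does not distinguish observations before and after MMF is stopped. Table 1 defines the primary endpoint as reservoir size when treatment ends.

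**The concern.** One event, failure of the month-12 check, has two incompatible consequences. A participant cannot both leave the study and stay in follow-up. No clause ranks the sections, and 6.1 is the visit procedure that clinic staff would use.

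Each reading has its own cost. Under 6.1, the draws after month 12 are never taken from those who fail, so late reservoir data come only from those who passed. With five participants, no control group (8.3) and no replacement of failures (9.0), the gap cannot be filled. Under 6.4, the draws can be taken, but 8.6 would analyse them as though MMF were still being given.

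**Working it through.** **The plan's own figure.** Section 8.4.1 gives a decline on ART alone of 0.0068 log10 IUPM per month. 12 × 0.0068 = 0.0816, stated as 0.082 per year; 1 − 10^(−0.0816) = 17.1%, stated as 17%. Both reproduce. The annualised SD of 0.2 is 12 × 0.017 = 0.204.

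**Which draws are at stake.** Section 6.1 puts the visits after month 12 at months 15, 18½ and 22, which are weeks 60, 74 and 88 in Table 2. Row labels are missing from that part of the table, so rows were matched by order and checked against the printed totals (mL):
- Weeks 60 and 74, trough: 3 + 3.5 + 4 + 3.5 + 20 + 3.5 + 212.5 + 5 = 255, as printed.
- Week 88, trough: 3 + 3.5 + 4 + 3.5 + 0 + 100 + 3.5 + 119 + 5 = 241.5, as printed.
- Week 90: 3 + 3.5 + 4 + 3.5 = 14, as printed, with no ACD or QVOA volume.

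The ACD tubes, whose uses include the ca-DNA assay, are 212.5, 212.5 and 119 mL. The 100 mL at week 88 is the QVOA.

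**Loss if 6.1 is followed.** Five participants × 3 visits = 15. Each failure removes 3 of 15 (20%) and one of five week-88 QVOAs. One to four failures remove 3, 6, 9 or 12 visits.

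**How likely a failure is (illustration).** Assume that the 12-month ca-DNA change is normal with SD 0.2 log10, a figure the plan gives only for IUPM. Then P(fail) = Φ((0.25 − μ)/0.2), where μ is the true mean fall, and P(at least one of 5) = 1 − (1 − P)^5:
- μ = 0.082: P = 0.80; at least one, above 0.99
- μ = 0.25: P = 0.50; at least one, 0.97
- μ = 0.35: P = 0.31; at least one, 0.84
- μ = 0.50: P = 0.11; at least one, 0.43

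**Distortion if 6.4 is followed.** Section 8.6 introduces the slope as a measure of reservoir change but writes it in log viral load; it is taken here to apply to ca-DNA, the main outcome in 8.2.1. Suppose the true slope is b1 up to month 12 on MMF and b2 afterwards. A straight line fitted to all points has expected slope b1 + w(b2 − b1), where w = Σ(t − t̄)(t − 12)₊ / Σ(t − t̄)². The draw times up to month 12 are an assumption, because that part of Table 2 is not legible.
- Months 0, 3, 6, 9, 12, 15, 18.5, 22: t̄ = 10.69; numerator 4.3125×3 + 7.8125×6.5 + 11.3125×10 = 176.84; denominator 407.47; w = 0.43.
- Months 0, 6, 12, 15, 18.5, 22: t̄ = 12.25; numerator 2.75×3 + 6.25×6.5 + 9.75×10 = 146.38; denominator 330.88; w = 0.44.

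Take a participant who just misses the criterion (about 0.25 log per year on MMF) and then declines at the ART-alone rate of 0.082. The fitted fall is 0.25 − 0.43 × (0.25 − 0.082) = 0.18 log per year, about 0.07 too small. The bias reverses if the on-drug fall was slower than the later one. The mixed model would weight the points differently but has the same gap, since arm is fixed for each person.

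**The case against.** The best reply is that 6.4 is the specific rule, that 8.1 and 9.0 fit it, and that 6.1 is one loose sentence. The data at risk also answer no stated objective: the endpoint is reservoir size when treatment ends, which for a failure is the month-12 value, collected under either reading. The selection of on-drug data after month 12 comes from the go/no-go rule itself. All of this stands. It limits the consequence but leaves the contradictory instruction and the gap in 8.6.

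A reader might infer more in four places, and the documents do not support it.
- **6.6 as a separate conflict.** It covers people who withdraw. If 6.4 governs, a go/no-go failure has not withdrawn, so 6.6 needs only a clarification.
- **All 15 late visits lost to this wording.** Section 6.5 lists absence of efficacy at one year in every participant as a ground for cancelling the study, so the draws might end then whatever 6.1 says.
- **No reservoir measurement at all for those who leave.** The last column of Table 2, PreDC (apparently premature discontinuation), seems to carry 20 mL for the low-level viral load. It shows no ACD or QVOA volume.
- **Conflicting thresholds or a stray second check.** Section 6.1 is silent on the threshold; 0.25 log is in 6.4 and 8.1, and ca-DNA in 3.0. The two-year check most naturally means month 22.

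**Conclusion.** The concern holds as an inconsistency between 6.1 and 6.4, with a linked gap in 8.6. If 6.1 is followed, each failure costs three ca-DNA draws and one QVOA, all off-drug. If 6.4 is followed, the off-drug slope takes about 43% to 44% of the weight in that participant's regression, under the assumed draw times and a single change of slope at month 12. The two harms are alternatives and should not be added together.

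The primary endpoint is not lost, and keeping the draws adds no on-drug information. Their value is that they are the main scheduled ca-DNA and QVOA data after MMF stops, because those who complete treatment have no such draw after week 88. How many will fail is unknown; 9.0 allows for anything up to all five. The 6.1 versus 6.4 conflict rests on the text alone; the failure probabilities and the slope weight are illustrations. It should be fixed before the first participant reaches month 12.

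**What to change.** - **6.1:** replace the two sentences on the yearly check with a cross-reference to 6.4.
- **6.4:** state that the criterion refers to ca-DNA, and that those who miss it stop MMF but keep the week 60, 74 and 88 trough reservoir draws, including the week-88 QVOA, unless they decline. Peak draws can be dropped off drug.
- **6.6:** clarify that these participants have not withdrawn.
- **8.6:** exclude observations after MMF stops from the on-MMF slope, or give them a separate off-drug slope.

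The cost is wording in four sections, with no new visits or assays. The burden is three off-drug draws of 241.5 to 255 mL, already scheduled and each below the 270 mL single-draw limit in 9.0. They fall 14 weeks apart, so no two share an eight-week window under the 450 mL limit.

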6.2 Toxicity

The participants will undergo standardized clinical evaluations at each visit. The evaluations will include an interim medical history, symptom-directed exam, assessment of concomitant medications, and collection of data on adverse events. Women of childbearing potential will undergo urine pregnancy tests at eligibility, enrollment and at each safety visit. Since MMF is FDA pregnancy category D, women involved in activity that could result in pregnancy will be required to use two forms of contraception. If women become pregnant during the study and are on a study medication, they will

Clinical Protocol

discontinue the medication immediately, and have no additional anoscopies if enrolled in the sub-study. Women will be asked, but will not be required, to allow the study staff to contact them after delivery to get information about their pregnancy outcome. Pregnant participants will be linked to care appropriate for pregnant women with HIV infection.

Participants will be closely monitored in a standardized fashion for potential toxicities and adverse events. Safety labs, including complete blood count, comprehensive metabolic panel, plasma HIV RNA concentrations and CD4 T cell counts will be monitored frequently as indicated in **Figure 1** and **Table 2**.

The Division of AIDS Table for Grading the Severity of Adult Adverse Events (DAIDS AE Grading Table), Version 1.0, dated December 2004, Clarification August 2009, will be used for screening eligibility and for grading toxicities and is available at <http://rsc.tech-res.com/safetyandpharmacovigilance>. Alternate explanations for clinical or laboratory abnormalities that may at first appear to be related to the study agent must be explored.

Management of adverse experiences will be according to the best clinical practice and the judgment of the site investigator. Participants with Grade 3 and 4 laboratory abnormalities will be asked to return to the clinic to have the test that is abnormal repeated, preferably within 72 hours. Laboratory norms will be the institutional values of the lab performing the tests. Abnormal clinical and laboratory findings will be followed until resolution to < Grade 2 or baseline.

- Grade 1 – Continue study drug; routine monitoring.
- Grade 2 – Continue study drug; monitor closely with more frequent visits when clinically indicated.
- Grade 3 – Continue study drug while awaiting confirmatory results unless the clinician believes that remaining on study drug would be unsafe. In this case, proceed as below.
- Confirmed Grade 3 events – Study drug should be discontinued until resolution to \leq Grade 2, unless the site investigator has compelling evidence that the toxicity is definitely NOT related to study drug. The event must be discussed with Drs. [name] and [name] and then must be reviewed weekly until the toxicity resolves to \leq Grade 2. If the event is possibly, probably, or definitely related to study drug but resolves to \leq Grade 2 in less than 7 days, study drug can be restarted. If the toxicity worsens over the next 7 days or does not resolve to \leq Grade 2 within 14 days, the study drug must be permanently discontinued. If the toxicity recurs or evolves to \geq Grade 3, the study regimen must be permanently discontinued.
- Grade 4 (even before confirming) – The study drug must be discontinued unless the site investigator has compelling evidence that the event is not due to study drug. Drs. [name] and [name], and the DSM panel, must be promptly notified of all Grade 4 events. Study drug will be permanently discontinued in the event of an adverse event \geq Grade 4 that is possibly, probably, or definitely related to study drug. Subjects experiencing adverse events requiring permanent discontinuation of drugs should be followed at least weekly until resolution of the adverse event to \leq Grade 2 or until stabilized and no longer in need of such frequent monitoring, as determined by the site investigator.

6.3 Reporting Requirements

Clinical Protocol

Grade 2 events should be recorded on CRFs at each visit and will be assessed for relationship to study drug.

Grade 3 or 4 events

- Subjects should have abnormal laboratory tests repeated as soon as possible, preferably within 72 hours (to determine if the result was spurious).
- [name] and [name] must be notified of confirmed \geq Grade 3 adverse events within 24 hours, if they are possibly, probably or definitely related to the study.
- The sponsor (American Foundation for AIDS Research or amfAR) will be notified of \geq Grade 3 adverse events within one week, if they are possibly, probably or definitely related to the study.

6.4 Criteria for Treatment and Individual Study Participant Discontinuation

- The subject requires treatment with disallowed medications
- Pregnancy
- Nausea, vomiting or diarrhea refractory to anti-emetic medications
- Drug toxicity that requires permanent study drug discontinuation as defined in Section 6.2.
- If a participant does not plan to continue with the study
- Go / no-go criterion at month 12: participants must have at least a 0.25 log reduction from baseline at 12 months to continue on MMF. If this criterion is not met, participants will continue to be followed off study drug.
- Subject stops their antiretroviral therapy regimen for greater than 2 weeks
- The subject refuses further treatment and/or follow-up evaluations and decides to discontinue participation in the study
- The investigator determines that further participation would be detrimental to the subject's health or well-being
- The subject experiences virologic failure. Virologic failure will be managed according to local guidelines. In this study, virologic failure is defined as plasma HIV RNA \geq 1,000 copies/mL (confirmed by repeating the assay on 2nd aliquot of the same specimen). If a participant has a viral load between 500-1000 HIV RNA copies, then we will call the participants for an immediate recheck of their viral load as soon as possible and will continue to do so, until this value normalizes or meets criteria for virologic failure. Of note, viral load may be checked by the participant's primary care provider outside of the study: these values will be available to the study PI and the criteria for virologic failure will be the same.
- The subject fails to comply with the study requirements so as to cause harm to him/herself or seriously interfere with the validity of the study results

6.5 Criteria for Study Discontinuation

Clinical Protocol

- The study is cancelled at the discretion of the IRB, DSMB and / or study PIs. This decision will be based on several possible factors including mild-moderate adverse effects in multiple participants, a severe adverse reaction in a single participant, and / or lack of 1-year efficacy in all participants.

6.6 Protocol for Study Discontinuation

Participants who withdraw from the study based on criteria described in sections 6.4 and 6.5 will be asked to return for a clinic visit for laboratory and safety tests. This procedure will continue until normalization of test results.

6.7 Replacement of Study Subjects

- All participants are strongly encouraged to attend all study visit dates, however if a participant misses an appointment they will be contacted until they can re-schedule the appointment or request being discharged from the study. If a participant misses 3 consecutive visits, they will be considered “lost-to-follow-up”.
- Replacement of participants. Considerable effort will be invested in maintaining participants in the study. New enrollee replaces a participant when a participant:
 - discontinues during the first six months of the study
 - is lost to follow-up during the first three months of the study
 - is unable to tolerate either MMF or Myfortic© during the lead-in phase of the study (Steps 1, 2a & 2b)
 - does not develop an adequate anti-proliferative effect on MMF or Myfortic© during the lead-in phase (Steps 2a & 2b)

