Study Population	HIV infected individuals on ≥2 years of suppressive ART who will specifically need to have demonstrated full viral suppression with at least four negative plasma viral loads with no more than one documented viral blip during this time.
Study Site	University of Washington AIDS Clinical Trials Unit (UW ACTU) at Harborview Medical Center in Seattle
Study Design	A prospective, open label trial
Study Duration	Accrual will require approximately 2 months. Each enrolled participant will be followed for 22 months
Study Agent	Mycophenolate mofetil or Myfortic©
Treatment Duration	22 months
Primary Objective	Establish the impact of prolonged anti-proliferative therapy on the HIV reservoir. We will test the following hypotheses: 
1. MMF or Myfortic© therapy will lead to a progressive decrease in reservoir size over 22 months of treatment.2. MMF or Myfortic© therapy will lead to a continual shift in HIV reservoir composition from primarily effector memory CD4+ T cells (T_{em}) and central memory CD4+ T cells (T_{cm}) to primarily stem cell like memory (T_{scm}) and naïve (T_n) CD4+ T cells.3. MMF or Myfortic© will eliminate detectable measures of the HIV reservoir, including by cell-associated DNA/mRNA and quantitative viral outgrowth.
Secondary Objectives	Establish the safety of prolonged MMF or Myfortic© therapy in 5 chronically HIV-1 infected patients whose viral loads are fully suppressed by ART.

Clinical Protocol

	
We will test the following hypotheses:
 
1. MMF or Myfortic© will be well-tolerated and will not decrease adherence to or antiviral efficacy of ART.2. Peripheral CD4+ T cell counts and percentages will not meaningfully decrease during treatment with MMF or Myfortic© and ART.3. There will be no excess risk of opportunistic infections in MMF or Myfortic© treated study participants.
Endpoint	The primary endpoint of the study is HIV reservoir size at the end of drug treatment.

Clinical Protocol

Figure 1: Study schema

Clinical Protocol

Table 2. Schedule of study visits and blood draws

ACTU-2100 MMF Study Schedule of Events						
VERSION 6						
TEST/TIMING	Eligibility	Entry	MMF 500mg QD LEAD-IN / STEP 1			IF NO ANTI-PROLIFERATIVE EFFECT, MMF 750mg BID LEAD-IN / STEP 2b
			week 1	week 2 T	week 2 P	
2018 Flu Vaccine month 6~12						
Flu vaccine response evaluation						
Rectal Biopsies OPTIONAL (to [name] Lab)			BIOP			
Complete Interview/Complete PE	X					

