2.0 STUDY HYPOTHESES AND OBJECTIVES

2.1 Hypotheses

- 2.1a MMF or Myfortic[©] will be well tolerated and will not decrease adherence to or antiviral efficacy of ART.
- 2.1b Peripheral CD4+ T-cell counts and percentages will not meaningfully decrease during treatment with MMF or Myfortic[©] and ART.
- 2.1c There will be no excess risk of opportunistic infections in MMF or Myfortic[©] treated study participants.
- 2.1d MMF or Myfortic[©] therapy will lead to a progressive decrease in reservoir size over 22 months of treatment.

Clinical Protocol

- 2.1e MMF or Myfortic[©] therapy will lead to a continual shift in HIV reservoir composition from primarily effector memory CD4+ T-cells (T_{em}) and central memory CD4+ T-cells (T_{cm}), to primarily stem cell like memory (T_{scm}) and naïve (T_n) CD4+ T-cells.
- 2.1f MMF or Myfortic[©] will eliminate detectable measures of the HIV reservoir, including cell-associated DNA/mRNA, and quantitative viral outgrowth.
- 2.1g MMF or Myfortic[©] will not decrease the humoral immune response to routine annual influenza vaccination.

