4.0 SELECTION AND ENROLLMENT OF SUBJECTS

4.1 Inclusion Criteria

- a. Confirmed HIV infection, by two different positive antibody tests and/or detectable plasma HIV RNA on two different dates
- b. ≥ 18 and ≤ 65 years of age
- c. Continuous ART during the last two years, with current ART preferably including an integrase inhibitor
- d. HIV RNA <40 copies / mL on four occasions during continuous ART of ≥ 2 years with no more than one blip of <1000 HIV RNA copies / mL
- e. CD4+ T cell count $> 350/\text{mm}^3$ within the past 365 days
- f. Karnofsky score ≥ 80
- g. Plan to reside in area 2 years
- h. Consents to study
- i. “Step 1” lead-in phase: Tolerability of MMF during one week dose escalation of 500 mg once daily (or Myfortic \odot 360 mg once daily)

Clinical Protocol

- j. "Step 2a" lead-in phase: Demonstrated tolerability and anti-proliferative effect (>= 80% anti-proliferative effect) of one week of MMF 500 mg twice daily (or Myfortic[®] 360 mg twice daily)
- k. "Step 2b" lead-in phase (only if necessary based on inadequate anti-proliferative effect on 500 mg bid): Demonstrated tolerability and anti-proliferative effect (>= 80% anti-proliferative effect) of one week of MMF 750 mg twice daily (or Myfortic[®] 540 mg twice daily)

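### No safety set is defined, lead-in tolerability is an entry criterion and lead-in intolerance leads to replacement, so judging tolerability in the final five would leave out early intolerance by design

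*Combined protocol and SAP*

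**What the plan says.** Section 4.1 lists the lead-in steps among the inclusion criteria. Criterion (i) is "Tolerability of MMF during one week dose escalation of 500 mg once daily" or the Myfortic equivalent. Criteria (j) and (k), for Step 2a and (if needed) Step 2b, each begin "Demonstrated tolerability and anti-proliferative effect".

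Section 6.7 provides for a new enrollee when a participant "is unable to tolerate either MMF" or Myfortic in lead-in Step 1, 2a or 2b. It does the same when a participant "discontinues during the first six months of the study".

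Section 9.0 continues screening and testing until five people have passed the anti-proliferation test. It expects about 1 in 5 starters to fail that test and describes them as not enrolled, although they have been dosed. It also says that people who stop MMF because of treatment-related side effects are not replaced.

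The secondary objective in the Protocol Summary is to "Establish the safety of prolonged MMF or Myfortic© therapy in 5 chronically HIV-1 infected patients". Hypothesis 2.1a is that the drug "will be well tolerated and will not decrease adherence to or antiviral efficacy of ART". The Aim two text in section 8.6 restates the tolerability hypothesis for healthy, suppressed participants. It gives no analysis set, denominator, threshold or estimator.

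**The concern.** Read together, these provisions select the five on part of the outcome that 2.1a is meant to assess. Someone who takes the drug, cannot tolerate either formulation and leaves during the lead-in is replaced, and the group described at the end contains only people who got through it. A statement that the drug was well tolerated in five patients would then be partly true by construction.

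The reservoir hypothesis in sections 3.0 and 8.6 is openly limited to participants with a demonstrated anti-proliferative response. The tolerability hypothesis carries no such limit and reads as a claim about suppressed patients in general. What is at stake is whether the result can be applied to people starting the drug. With five places, one omitted person changes the reported proportion materially.

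**Working it through.** The plan states no figure for tolerability, so there is none to reproduce. The check sets the rules side by side and then sizes the possible effect.

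**Window removed.** Under section 5.1, Step 1 lasts one week and Step 2a two weeks, with the decision at week 3. Step 2b, where used, runs to the decision at week 5. The lead-in therefore covers 3 to 5 weeks, against a schedule in which month 22 is week 88.

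**Further window under 6.7.** Replacing discontinuations in the first six months also covers stops for intolerance after the lead-in. Section 9.0 says side-effect stops are not replaced and does not expressly limit this to the time after Step 3.

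**Same data, two denominators.** Let k be the number who fail the lead-in for intolerance, with no later intolerance. Let a be the number who fail the anti-proliferation test; they were dosed and belong in an all-dosed denominator. The five always show 0/5. All dosed show k/(5 + k + a). Exact (Clopper-Pearson) 95% limits:

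| k | Final five | All dosed, a = 0 | All dosed, a = 1 |
|---|---|---|---|
| 1 | 0/5 = 0% (0 to 52%) | 1/6 = 17% (0.4 to 64%) | 1/7 = 14% (0.4 to 58%) |
| 2 | 0/5 = 0% (0 to 52%) | 2/7 = 29% (4 to 71%) | 2/8 = 25% (3 to 65%) |
| 3 | 0/5 = 0% (0 to 52%) | 3/8 = 38% (9 to 76%) | 3/9 = 33% (7 to 70%) |

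**How likely each k is.** The documents give no lead-in intolerance rate, so q is an assumption. Ignoring anti-proliferation failures:

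- P(at least one intolerance failure before five pass) = 1 − (1 − q)^5
- P(three or more) = 1 − (1 − q)^5 × (1 + 5q + 15q²)

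| Assumed q | At least one | Three or more |
|---|---|---|
| 5% | 23% | 0.4% |
| 10% | 41% | 2.6% |
| 20% | 67% | 15% |
| 30% | 83% | 35% |

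For q = 10%: 1 − 0.9^5 = 1 − 0.590 = 0.410, and 1 − 0.5905 × (1 + 0.5 + 0.15) = 1 − 0.974 = 0.026.

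If 1 in 5 of those who tolerate the drug fail the anti-proliferation test, more starters are needed. Among starters who either pass or are intolerant, the chance of passing is 0.72/(0.72 + 0.10) = 0.878. The chance of at least one intolerance failure becomes 1 − 0.878^5 = 48%, and of three or more about 4%.

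**With later intolerance too.** If a proportion r of those who pass become intolerant later, the five show r in expectation, while all who start and do not fail for lack of anti-proliferative effect show q + (1 − q)r. With q = 10% and r = 10%, that is 10% against 0.10 + 0.90 × 0.10 = 19%.

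**The case against.** The strongest reply is that the plan states no tolerability denominator, so it cannot be said to prescribe a biased one. That stands. Section 6.1 enrolls people at the Entry visit, when the first drug is given. Section 6.7 calls lead-in failures participants. Section 6.2 collects adverse events at every visit, section 6.6 recalls withdrawals for safety tests, and section 8.5 has the monitoring board review the safety and tolerance of all interventions. A reader might infer that tolerability will be tested only in people already shown to tolerate the drug, or that following the plan exactly yields the biased figure. The documents do not support that: nothing discards lead-in safety data, and the restriction to the five is inferred from the wording of the objective and the missing safety set.

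Second, the objective concerns prolonged therapy, and people who cannot complete a lead-in cannot inform it. That also stands. A disclosed run-in is legitimate, and it removes only the first weeks; sections 6.2 and 6.4 still capture later intolerance. It does not answer 2.1a, which is not limited to those who pass.

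Third, the scenarios are assumed, the intervals overlap heavily, and three or more failures would be uncommon at 10%. True. Section 1.3 reports nausea in fewer than 10% in other settings, but that is not an intolerance rate and cannot fix q. The argument rests on direction and on the ease of avoiding the problem, not on a predicted size.

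A reader might also count a switch to Myfortic as intolerance. The documents do not support that either: 2.1a covers both formulations, section 6.1 plans the switch, and 6.7 counts a lead-in failure only when neither is tolerated. Nor can sections 6.7 and 9.0 be taken to agree about lead-in failures, given the unqualified wording in 9.0.

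**Conclusion.** The point holds in conditional form. If 2.1a is judged in the five patients named in the safety objective, lead-in intolerance is excluded by design and the result is biased in the drug's favour. Nothing in section 8.6 prevents this. The direction follows from 4.1, 6.7 and the objective and needs no assumption. The size does: for one to three lead-in intolerance failures and no later intolerance, the contrast is 0% in the five against 14% to 38% among all dosed, and at an assumed 10% rate there is about a 41% chance that at least one such failure occurs. Intolerance after the lead-in can still be seen, subject to the six-month replacement rule. This is a gap in analysis and reporting on a secondary objective. The data needed to close it are already collected, and it should be closed before the results are summarised.

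**What to change.** - In section 8.6, define the safety and tolerability set as everyone who took at least one dose of MMF or Myfortic. Name lead-in intolerance failures, anti-proliferation failures and all replaced participants as included.
- Report permanent stops for intolerance over number dosed, by lead-in step and after Step 3, with an exact 95% interval.
- Report switches to Myfortic as a separate count, not as failures.
- Describe any result in the five as tolerability of prolonged therapy among people who passed the lead-in.
- Reconcile sections 6.7 and 9.0 on whether people who stop because of side effects are replaced, and state the period to which each rule applies.

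Cost: a few sentences in 8.6, one more table row and one cross-check between two sections. No change to dosing, visits, samples, eligibility or the lead-in is needed. The downside is a tolerability figure that may be less favourable.
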